2.1 Primary Objective

The primary objectives of this study are to evaluate the safety, tolerability and efficacy of multiple doses of CAM-3001 administered SC in subjects with at least moderately active RA.

2.2 Secondary Objectives

The secondary objectives of this study are:

- 1) To evaluate clinical outcomes in RA
- 2) To explore CAM-3001 dose and the relationship with safety and efficacy
- 3) To evaluate the PK and immunogenicity of CAM-3001

2.3 Exploratory Objectives

The exploratory objectives of this study may include the following:

- 1) To investigate the effects of CAM-3001 on:
 - Expression of proteins such as GM-CSF, biomarkers of disease activity, autoantibodies and other inflammatory proteins in serum
 - The potential relationships between inhibition of GM-CSF-inducible gene signature, clinical activity, GM-CSF receptor occupancy and drug concentration (PK) and the miRNA and/or mRNA expression pattern in the periphery of subjects enrolled.
 - Patient reported outcomes
- 2) To assess whether deoxyribonucleic acid (DNA) polymorphisms are associated with the safety or clinical response to CAM-3001 (optional for subjects)

3 Study Design

3.1 Overview of Study Design

This is a multicentre, randomised, double-blind, placebo-controlled study to evaluate the efficacy and safety of multiple ascending SC doses of CAM-3001 in combination with stable methotrexate in subjects aged 18 to 80 years of age with active RA.

Protocol MI-CP219; Amendment 3 Final

Approximately 72 sites worldwide may be involved in the study. A total of 216 subjects will be recruited into 4 cohorts of 54 subjects to receive either 10 mg, 30 mg, 50 mg or 100 mg SC doses of CAM-3001 or placebo every other week for 12 weeks. All cohorts will be randomised in a 2:1 ratio (active:placebo). For Cohorts 1 to 3, decisions relating to dose escalation will be made by the sponsor (including the medical monitor, the safety physician, the project medical director and additionally final approval by the MedImmune Safety Monitoring Committee (SMC) which includes internal and external experts). These reviews of all cumulative safety data will occur after at least 18 subjects have completed dosing on Day 29. In Cohort 4, an initial 18 subjects will be recruited; once at least 6 of these subjects have been exposed to investigational product for the entire treatment period (Day 85) and no safety concerns have been detected, randomisation will resume to enrol the remaining number of subjects planned for this cohort.

Additional subjects will be recruited at sites in Japan. A total of 48 subjects from Japan will be randomised into 4 cohorts in a 2:1 ratio (active:placebo) with a total of 12 subjects per cohort. Details are included in a local protocol amendment for Japan.

The assigned dose of CAM-3001 or placebo (1 mL) will be administered as SC injections in the upper arm, thigh, or abdomen. The intention of the protocol is that subjects will be maintained on the same stable dose of concomitant RA treatment from Screening until Day 85. Adverse events and SAEs will be collected from the time of consent until the end of the safety follow-up period. Disease activity will be assessed throughout the treatment period and during safety follow-up. The schedules of subject evaluations are presented in Table 5.2-1.

Cumulative safety data will be reviewed by the sponsor continuously throughout the study. Formal safety reviews will include all subjects in the study at the data cut-off irrespective of the number of doses that subjects have received at that point.

Cohort 1

For cohorts 1 to 3, dose escalation to the next cohort will occur after at least 18 subjects have completed dosing on Day 29.

In cohort 4, an initial 18 subjects will be recruited (12 CAM-3001 and 6 placebo). Once at least 6 of these subjects have been exposed to study treatment for the entire treatment period (Day 85) and no safety signals have been detected, recruitment will resume and complete.

* In each cohort, 12 Japanese subjects will be recruited (8 CAM-3001 and 4 placebo)

In Japan, the dose escalation decision (all cohorts) will be made based on a review of all cumulative safety data available after 6 Japanese subjects have completed dosing on Day 29.

Figure 3.1-1 **Study Flow Diagram**

D = days; F/up = Follow-up

The endpoints to be measured in this study are described in Section 7.3.

3.2 **Estimated Study Duration**

Screening evaluations will be carried out within 28 days prior to randomisation. The treatment period for each cohort will be to Day 85 ± 2 days. This will be followed by a safety follow-up period of 12 weeks ± 1 week.

MedImmune CAM-3001 4 Study Procedures

4.1 Subject Participation and Identification

Study participation begins once written informed consent is obtained (see Section 10.3 for details). Once informed consent is obtained, a subject identification number will be assigned by a central system (eg, an interactive voice/web response system, IVRS/IWRS), and the screening evaluations may begin to assess study eligibility (inclusion/exclusion) criteria. The subject identification number will be used to identify the subject during the screening process and throughout study participation, if applicable.

A master log of all consented subjects will be maintained at the site and will document all screening failures (ie, subjects who were consented but did not meet study eligibility criteria and/or were not randomised), including the reason(s) for screening failure (see Section 9.1 for details).

4.2 Subject Selection

The subjects in this study will be male or female adults with RA as defined by the 1987 American College of Rheumatology (ACR) classification criteria, and at least moderately active disease, as defined by Disease Activity Score (DAS) 28 criteria (DAS \geq 3.2), despite treatment with methotrexate for at least 12 weeks prior to Screening, which has been kept at a stable dose for at least 4 weeks (7.5 to 25 mg/week).

The investigator (physician) or qualified designee will discuss the study with a subject who is considered a potential candidate for the study and provide the subject with the study-specific informed consent form approved by the Institutional Review Board (IRB)/ Independent Ethics Committee (IEC). The investigator or designee will address any questions and/or concerns that the subject may have and, if there is continued interest, will secure written informed consent for participation in the study. Written informed consent and any locally required authorisation (eg, Health Insurance Portability and Accountability Act [HIPAA] authorisation in the USA, European Union [EU] Data Privacy Directive authorization in the EU), will be obtained prior to conducting any protocol-related procedures, including screening evaluations. See Section 10.3 for additional details concerning informed consent.

MedImmune CAM-3001 **4.2.1** Inclusion Criteria

Subjects must meet *all* of the following criteria:

- 1) Male or female
- 2) Age 18 through 80 years at the time of Screening
- 3) Signed and dated informed consent, prior to receipt of any study medication or any study related procedures.
- 4) A diagnosis of adult onset RA of at least 3 months duration as defined by the 1987 ACR classification criteria (Arnett et al, 1988).
- 5) Treatment with methotrexate (7.5-25 mg/week) for at least 12 weeks and at stable and tolerated doses for at least 4 weeks prior to Screening.
- 6) Positive anti-cyclic citrullinated peptide (CCP) IgG antibodies (> 5 IU/mL) and/ or rheumatoid factor (> 14 IU/mL) at Screening.
- 7) Subjects must receive \geq 5 mg/week folic acid as a single or divided dose during the study.
- 8) At least moderately active disease as defined by $DAS28 \ge 3.2$ at Screening and Baseline (see Section 5.3.4.1; Smolen et al, 2003).
- 9) a) Females of childbearing potential; unless surgically sterile (ie, bilateral tubal ligation, bilateral oophorectomy, or complete hysterectomy), has a sterile male partner, is premenarchal or at least 2 years postmenopausal, or practices abstinence; must use 2 effective methods of avoiding pregnancy (including oral, transdermal, or implanted hormonal contraceptives, intrauterine device, female condom with spermicide, diaphragm with spermicide, cervical cap with spermicide, or use of a condom with spermicide by the sexual partner) for 21 days prior to randomisation and at Day 1, and must agree to continue using such precautions until the end of the 12 weeks safety follow-up; cessation of birth control after this point should be discussed with a responsible physician. A negative pregnancy test is required both at Screening and prior to dosing.

b) Males, unless surgically sterile, must use 2 effective methods of birth control with a female partner and must agree to continue using such contraceptive precautions from Screening through the end of the 12 weeks safety follow-up.

- 10) No evidence of medically significant respiratory disease. A local pulmonologist will review subjects' respiratory system including, chest x-ray, pulmonary function, and diffusing capacity for carbon monoxide (DLCO), which are performed at Screening. Subjects must have:
 - DLCO \geq 80% predicted value
 - Forced expiration volume in first second (FEV₁) by spirometry $\ge 80\%$ predicted value

MedImmune	Protocol MI-CP219; Amendment 3
CAM-3001	Final
•	No pneumonitis and clinically significant obstructive or restrictive lung

11) Willing and able to comply with the protocol and complete the study period.

4.2.2 Exclusion Criteria

Any of the following would exclude the subject from participation in the study:

Relating to Rheumatoid Arthritis

- 1) A rheumatic autoimmune disease other than RA, or significant systemic extraarticular involvement secondary to RA (including but not limited to; vasculitis, pulmonary fibrosis, or Felty's syndrome). Subjects with secondary Sjögren's syndrome or secondary limited cutaneous vasculitis with RA are eligible.
- 2) A history of, or current, inflammatory joint disease other than RA (eg, gout, reactive arthritis, psoriatic arthritis, seronegative spondyloarthropathy, Lyme disease) or other systemic autoimmune disorder (eg, systemic lupus erthymatosus, inflammatory bowel disease, scleroderma, inflammatory myopathy, mixed connective tissue disease or other overlap syndrome).
- 3) Functional class IV defined by the 1992 ACR Classification of Functional Status in RA (Hochberg et al, 1992).

Relating to Concomitant Medications, Previous Biologic and Non-biologic Treatments

- 4) Treatment with any investigational drug therapy within 28 days or 5 half-lives of the drug, whichever is longer, prior to Screening.
- 5) Previous treatment with > 1 biologic therapy for RA that was discontinued for lack of efficacy.
- 6) Any cell depleting therapies (eg, anti-CD20) within 12 months prior to Screening; or previous treatment with non-depleting biologic therapies (such as anti-TNF α , recombinant interleukin-1 receptor anatagonist, anti-interleukin-6, or abatacept) within 30 days or 5 half-lives (8 weeks for infliximab) of the biologic agent, whichever is longer, prior to Screening.
- 7) Previous administration of CAM-3001.
- 8) History of known allergy or reaction to any monoclonal antibody or any component of the CAM-3001/investigational product formulation.
- 9) Treatment with disease modifying anti-rheumatic drugs (DMARDs), other than background methotrexate, including sulfasalazine, azathioprine, cyclosporine, thalidomide, D-penicillamine, or tacrolimus within 28 days of Screening, and leflunomide within 12 weeks (or 28 days if after 11 days of standard cholestyramine washout) before Screening.

MedImmune

CAM-3001

- 10) Treatment with alkylating agents 12 weeks prior to Screening.
- 11) If receiving current treatment with non steroidal anti-inflammatory drugs (NSAIDS), these must be on a stable dose for ≥ 28 days prior to Screening and remain stable for the duration of the treatment phase of the study.
- 12) Intramuscular (IM), IV or intra-articular (IA) corticosteroids within 28 days before Screening.
- 13) Treatment with > 10 mg/day dose prednisone (or equivalent) within 28 days of Screening. Concomitant treatment with oral corticosteroids \leq 10 mg/day prednisone or equivalent is permitted providing that the dose is stable for \geq 28 days prior to Screening and remains stable for the duration of the treatment phase of the study.

Relating to Medical History

- 14) Female subjects who are pregnant, intend to become pregnant, or are breastfeeding.
- 15) Subjects who in the opinion of the investigator or qualified designee have evidence of active tuberculosis (TB), either treated or untreated, or latent TB without completion of an appropriate course of treatment or appropriate ongoing prophylactic treatment. Evaluation will be according to the local standard of care and will consist of history and physical examinations, chest x-ray, and TB test (eg, purified protein derivative [PPD]¹) testing, etc with the standard of care as determined by local guidelines.
- 16) Active infection including symptoms, signs suggestive of clinically significant infection, any significant recurrent or chronic infection (including positive HCV antibody and chronic active HBV infection), or any episode of infection requiring hospitalisation or treatment with IV antibiotics within 12 weeks before Screening. Subjects with any opportunistic infection within 6 months before Screening will be excluded from the study.
- 17) Subjects at a high risk of infection eg, a history of an infected joint prosthesis at any time with that prosthesis still in situ, leg ulcers, indwelling urinary catheter, persistent or recurrent chest infections.
- 18) History of hereditary or acquired immune deficiency disorder including a history of known HIV infection.
- 19) Receipt of live (attenuated) vaccine within the 28 days before Screening or during the study.
- 20) Any history of cancer except basal and squamous cell carcinoma of the skin or in situ carcinoma of the cervix treated and considered cured.
- 21) Any surgical procedure (except for minor surgeries requiring local or no anaesthesia and without any complications or sequelae), including bone or joint

¹ The TB test procedure will be agreed and documented by country and approved by MedImmune prior to recruitment.

surgery/synovectomy (including joint fusion or replacement) within 12 weeks prior to Screening or any planned surgery within 3 months after randomisation.

- 22) Any neurological (congenital or acquired), psychiatric, vascular, or systemic disorder that could also affect the evaluation of efficacy assessments; in particular, joint pain and swelling (eg, Parkinson's disease, cerebral palsy, diabetic neuropathy, chronic fatigue syndrome, or chronic remitting anaemia of unknown origin or requiring transfusion).
- 23) Significant respiratory or pulmonary disease including symptomatic lung fibrosis, pneumonitis, uncontrolled asthma, dyspnoea, malignancy and history of chronic respiratory tract infections.
- 24) Congestive heart failure New York Heart Association classification III or IV.
- 25) History of methotrexate or any drug induced lung fibrosis or pneumonitis.
- 26) History of deep space/tissue infection (eg, fasciitis, abscess, osteomyelitis, septic arthritis) within 12 months prior to Screening.
- 27) Evidence of any disease or history of any disease, any finding upon physical examination, or any clinically significant laboratory or radiographic abnormality that, in the opinion of the investigator, designated healthcare provider, or medical monitor, may compromise the safety of the subject in the study or confound the analysis of the data.
- 28) At Screening blood tests; any of the following:
 - Aspartate transaminase (AST) $> 2.5 \times$ upper limit of the normal range (ULN)
 - Alanine transaminase (ALT) $> 2.5 \times ULN$
 - Haemoglobin (Hb) < 8.0 g/dL
 - Neutrophils $< 1,500/\text{mm}^3$

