4.5.4.1 Modification of Treatments for RA

All changes to the RA treatment and the reasons for change must be clearly documented in the eCRF.
MedImmune CAM-3001 **Methotrexate and Corticosteroids**

Changes in ongoing RA treatment or introduction of new therapies are not allowed during the study period (Screening until Day 85). This includes the dose of methotrexate, corticosteroids and NSAIDS. After the Day 85 study visit, where possible the doses of background medication should be kept as constant as possible up to completion of the safety follow-up period (Day 169). Modifications to background RA medication will be permitted for safety reasons such as adverse reactions due to these medications (eg, gastrointestinal adverse events), and infectious diseases.

Subjects who require a change to their RA therapies for reasons other than safety, such as for poor disease control or worsening of their RA between Day 1 and Day 85 may be discontinued from dosing upon review by the medical monitor, but will remain in the study and be followed-up for safety. All study assessments should be completed, unless consent is withdrawn.

The risk/benefit to the subject should be carefully assessed and consideration given to the timing of any necessary dose modification or introductions of new medications during the study period and should be discussed with the medical monitor where possible.

Injection of IA corticosteroids is discouraged, but a maximum of 2 IA injections of corticosteroids (dose up to 40 mg of triamcinolone or equivalent) are allowed as needed to control joint flares during the treatment period of the study. Treated joints will not be counted for tenderness and swelling for 12 weeks post injection.

Analgesics

Analgesics and NSAIDS should be maintained at a stable dose for the duration of the study. Subjects should refrain from taking the usual morning dose of analgesics on visit days until after all clinical assessments have been completed (see Table 5.2-1 for Frequency of Assessments).

Disallowed Medications

The following medications are prohibited during the treatment period of the study:

- Any investigational agent other than CAM-3001
- Alkylating agents, including cyclophosphamide

MedImmune

CAM-3001

- Biologic agents or non-biologic DMARDS other than methotrexate
- Immunoabsorption columns, plasmapheresis and IV immunoglobulin therapy
- Live or live-attenuated vaccines

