Immunisation with any live or live attenuated vaccine (ie, measles, mumps, rubella and polio vaccine, Bacillus Calmette-Guérin (BCG), typhoid, yellow fever, cold adapted live influenza strain vaccine or any other vaccines not yet licensed but belonging to this category) is specifically excluded during the treatment period (Centers for Disease Control and Prevention, ACIP Recommendations, 1993).

Subjects who are eligible for yearly influenza vaccine or who require booster vaccinations for other diseases can receive vaccination with killed/toxoid vaccines consistent with normal clinical practice. The effect of CAM-3001 on vaccine response is not known.

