- 9) Assess modified Borg scale score and pulse oximetry
- Collect urine for pregnancy test; ensure result is negative 10)
- Administer investigational product 11)
- 12) Take vital signs (pre and postdose)

Day 43: Fourth Injection

Visit 6

Patient reported assessments:

Administer patient assessment of pain, patient global assessment of disease activity, 1) modified Borg scale, and HAQ-DI to subjects

Joint counts assessor (skilled arthritis assessor):

2) Perform tender and swollen joint count

- Assess for AEs and SAEs 3)
- Update concomitant medications 4)
- Complete physician global assessment of disease activity 5)
- Collect predose blood and serum for assessment of: 6)
 - Serum chemistry •
 - Haematology with differential platelets
 - Rheumatoid factor (including isotypes IgM, A and G) and anti-CCP antibodies •
- 7) Collect urine for urinalysis
- Assess modified Borg scale score and pulse oximetry 8)
- Collect urine for pregnancy test; ensure result is negative 9)
- 10) Administer investigational product
- Take vital signs (pre and postdose) 11)

MedImmune CAM-3001 Day 57: Fifth Injection

Visit 7

Patient reported assessments:

1) Administer patient assessment of pain, patient global assessment of disease activity, modified Borg scale, HAQ-DI and FACIT-Fatigue to subjects

Joint counts assessor (skilled arthritis assessor):

2) Perform tender and swollen joint count

Safety assessor (physician):

- 3) Assess for AEs and SAEs
- 4) Update concomitant medications
- 5) Complete physician global assessment of disease activity
- 6) Collect predose blood and serum for assessment of:
 - Serum chemistry
 - Haematology with differential platelets
 - Rheumatoid factor (including isotypes IgM, A and G) and anti-CCP antibodies
 - CAM-3001 serum concentrations
 - Anti-CAM-3001 antibodies
 - Whole blood for mRNA and miRNA analysis
 - Serum for exploratory biomarker studies
 - Whole blood for receptor occupancy analysis
- 7) Collect urine for urinalysis
- 8) Assess modified Borg scale score and pulse oximetry
- 9) Collect urine for pregnancy test; ensure result is negative
- 10) Administer investigational product
- 11) Take vital signs (pre and postdose)

Day 71: Sixth Injection

Visit 8

Same as Day 43 (Visit 6).

Protocol MI-CP219; Amendment 3 Final

MedImmune CAM-3001 Day 85: Seventh Injection

Visit 9

Same as Day 29 (Visit 5).

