6.3.1 Study Reporting Period for Adverse Events

The reporting period for AEs is the period immediately following the time that written informed consent is obtained through Day 169. Any AE that starts within the reporting period will be followed up to the end of the clinical study (Day 169). New nonserious AEs that start after the reporting period will not be collected.

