6.4.1 Interruption or Permanent Discontinuation of Study Dosing in Individual Subjects

Interruption of dosing

MedImmune

The investigator may interrupt dosing if the subject experiences an event which, in the opinion of the investigator or the medical monitor, compromises subject safety such as active infection, deterioration of cardiopulmonary diseases meeting the exclusion criteria specified in Section 4.2.2 or the development of other complications. A subject with a neutrophil count below 1.5×10^9 /L will not receive any further investigational product until resolution of these symptoms. Similarly, a subject with a deterioration of pulmonary function (spirometry) or DLCO of more than 20% of the baseline values will not receive any further investigational product until the tests are repeated and an evaluation is performed by the pulmonologist that confirms the absence of any clinically significant lung problem. This opinion must then be communicated to the medical monitor. If the medical monitor gives approval to continue dosing, the scheduled dose should be administered at the latest within 5 days of the visit date. If dosing is not possible within 5 days, then the dose will be skipped at this visit. The next scheduled dose will be administered according to the protocol visit schedule.

Discontinuation of dosing

An individual subject will not receive any further investigational product if any of the following occur in the subject in question:

- 1) Withdrawal of consent.
- 2) Pregnancy.
- 3) Event which in the opinion of the investigator or the sponsor contraindicates further dosing such as illnesses or complications.
- 4) Any serious or life-threatening AE related to the investigational product.

MedImmune

CAM-3001

- 5) A change in concomitant RA therapy or other restricted medication during the treatment period of the study as described in Section 4.5.4.
- 6) A neutrophil count below 1.0×10^9 /L after administration of investigational product.

Subjects who are permanently discontinued from investigational product will be followed for the full study period (through Day 169). Where possible all study assessments should be completed, unless consent is withdrawn.

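### The live-vaccine bar has two windows: exclusion 19 is best read as running to Day 169, but Section 4.5.4.1 stops at Day 85, the day of the last dose

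*Protocol*

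**What the plan says.** The protocol states the bar on live vaccine three times.

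- Section 4.2.2, exclusion 19: "Receipt of live (attenuated) vaccine within the 28 days before Screening or during the study".
- Section 4.5.4.1, Disallowed Medications: the list that contains live and live-attenuated vaccines opens with "The following medications are prohibited during the treatment period of the study".
- Section 4.5.4.1, the vaccine paragraph after that list: immunisation with any such vaccine "is specifically excluded during the treatment period".

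The two terms are given days elsewhere. Section 3.2 states: "The treatment period for each cohort will be to Day 85", with a window of 2 days either side, and then a safety follow-up of 12 weeks, plus or minus 1 week. Section 5.2.2 heads Visit 9 "Day 85: Seventh Injection", and it is the last of the seven doses. On the end of the study, Section 6.3.1 says that an adverse event "will be followed up to the end of the clinical study (Day 169"), and Section 6.4.1 says that subjects who stop dosing are "followed for the full study period (through Day 169").

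**The concern.** One safety prohibition should have one window. Here the exclusion appears to protect subjects to Day 169, while the rule for conduct during the trial stops at Day 85. Table 5.2-1 schedules the eligibility check at Screening and Day 1 only. A site asked about a live vaccine in follow-up would therefore turn to Section 4.5.4.1, which sets no restriction after the treatment period.

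The timing is awkward because Day 85 is itself a dosing day, so the bar lapses just as the subject has received a further dose. The protocol lists susceptibility to infection among its events of special interest (Section 4.5.5). Where it means a precaution to outlast dosing it says so: inclusion 9 requires contraception until the 12-week follow-up is over.

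What is at stake is subject safety and uniform conduct across sites, not the efficacy result.

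**Working it through.** No sample size, power or error-rate figure is involved. The check sets the texts side by side and counts days.

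**Step 1. End of the window in Section 4.5.4.1.** Both statements use the treatment period. By Section 3.2 this ends at Day 85, and by Section 5.2.2 Day 85 is the seventh injection. The bar therefore covers 0 days after the day of the last dose.

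**Step 2. End of the window in exclusion 19.** The criterion gives no day, so it has to be read from the rest of the protocol.

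- For Day 169: Sections 6.3.1 and 6.4.1 both end the study there. The lead-in in Section 4.5.4.1 treats the treatment period as one part of the study. Exclusions 11 and 13, in the same list, refer to the treatment phase when they mean the shorter window; exclusion 19 does not.
- For Day 85: Section 4.5.4.1, on changes to RA therapy, glosses the study period as Screening to Day 85. Its NSAID rule speaks of the whole study, where exclusion 11 speaks of the treatment phase. Section 5.3.1 restates exclusion 21 as a bar on scheduled surgery during the study, although exclusion 21 itself reaches only 3 months past randomisation.

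Day 169 is the better supported reading, but not the only possible one.

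**Step 3. Size of the difference on the better reading.**

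- Nominal: 169 - 85 = 84 days; 84 / 7 = 12 weeks, which equals the follow-up length in Section 3.2.
- With the follow-up tolerance of 1 week: 11 x 7 = 77 days to 13 x 7 = 91 days.

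**Step 4. Context only.** Section 1.5.1 expects free receptor to be nearly back at its starting level some 2 to 8 weeks after dosing stops. From Day 85 that is 85 + 14 = Day 99 to 85 + 56 = Day 141, within the 84 days. Section 1.5.1 uses this figure to justify the length of follow-up and does not mention vaccines.

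**The case against.** The strongest reply is that exclusion 19 does not plainly mean Day 169. It names no day, and the loose uses of the word study listed above are real. If it is read as ending at Day 85, all three statements agree and the inconsistency disappears; what is left is a preference for a longer bar. The first part stands, and the point is therefore put as the better reading, not the plain one. It does not dispose of the matter, because two explicit statements place the end of the study at Day 169 and the same exclusion list uses a different term for the shorter window.

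A second reply is that the rules do not collide, since a site can satisfy both by following the broader one. That is true. A reader might infer that Section 4.5.4.1 permits live vaccine after Day 85. It does not; it is silent. But a site has to notice an entry criterion, no longer checked after Day 1, in order to find the longer window.

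A reader might also take the receptor-recovery days as a measured period of vaccine risk. The protocol does not support that. It states no vaccine washout and says only that the effect on vaccine response is unknown. The step from receptor occupancy to live-vaccine risk is an inference, and it is weakest at 10 mg, where Section 1.5.1 predicts transient occupancy below 90%.

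Finally, the dosing-discontinuation rule in Section 6.4.1, which refers to "other restricted medication during the treatment period of the study as described in Section 4.5.4", settles nothing either way. It governs stopping doses, and no dose follows Day 85.

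Existing safeguards limit the consequence. Concomitant medications, expressly including vaccines, and adverse events are recorded through Day 169, and serious or opportunistic infections are monitored as events of special interest.

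**Conclusion.** The point holds as a minor inconsistency in a safety prohibition. On the better reading of exclusion 19, the on-study rule in Section 4.5.4.1 is 84 days shorter (77 to 91 days with the follow-up tolerance), and it lapses on the day of the last dose.

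This rests on taking the study in exclusion 19 to end at Day 169, as Sections 6.3.1 and 6.4.1 do. Only subjects given a live vaccine after Day 85 could be affected. The protocol gives no rate for that, so no number of subjects is claimed. There is no effect on the Day 85 efficacy analysis, and nothing here shows that harm is expected.

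**What to change.** In both places in Section 4.5.4.1, prohibit live and live-attenuated vaccines to the close of safety follow-up (Day 169). This matches exclusion 19 on its better reading and the contraception window in inclusion 9.

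In the Disallowed Medications list, attach the longer window to the vaccine item and leave the shared lead-in alone. The lead-in also governs biologics, other DMARDs and the remaining items, and changing it would extend those bars as well.

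The cost is two phrases in an amendment or clarification letter, with no added visits, procedures or subjects. The downside is that a subject may have to defer a live vaccine by up to 12 weeks after Day 85. Exclusion 19 already asks for this on its better reading; on the Day 85 reading it would be a new restriction.
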